### C.3.8 *Revisions in Patient Information and Informed Consent Form*

Medtronic will inform the investigators whenever information becomes available that may be relevant to the subject's continued participation in the trial. The revised information will be sent to the investigator for approval by the IRB/MEC. After approval by the IRB/MEC, a copy of this information must be provided to the participating subjects, and the informed consent process as described above needs to be repeated. The investigator or his/her designee should inform the subject in a timely manner.

C.3.9 Enrollment Flowchart for Randomization to TAVI or SAVR

**Figure 1: Enrollment Flowchart**

If the patient meets all of the inclusion criteria and none of the exclusion and Heart Team determines the patient is eligible for randomization in the SURTAVI trial, subjects will be randomized on a 1:1 basis to either TAVI or SAVR. Randomization will be stratified by the need for coronary revascularization. In case of required coronary revascularization, concomitant percutaneous coronary intervention (PCI) and TAVI is encouraged; however staging is left at the discretion of the operator. Coronary artery bypass graft (CABG) should be conducted during the index procedure.

**C.3.10 Trial Training**

Prior to investigational site activation or subsequent involvement in trial activities, Medtronic (or designee) will provide trial training relevant and pertinent to the involvement of personnel conducting trial activities, including investigator responsibilities, adverse event reporting as well as device training (if necessary, usage and handling of device under investigation). Training may be conducted via Site Initiation Visits, Investigator and Coordinator Meetings, and/or other

media sessions. The sponsor will maintain documentation of attendance at each of these training opportunities, as applicable.

Additionally, Medtronic representative(s) may be present at each site's TAVI procedures as part of the ongoing training process.

## C.4 Trial Procedures

### C.4.1 Screening Procedures

Prior to any trial-specific tests or procedures, written informed consent must be obtained from the subject. Failure to obtain a signed and hand dated informed consent prior to the procedure constitutes a protocol violation, which is reportable to the IRB/MEC, the Food and Drug Administration (FDA), and other regulatory authorities as applicable.

All potential subjects for trial entry must be screened for eligibility. All patients with symptomatic severe AS that provide informed consent will be entered into the Electronic Data Capture (EDC) system and total number of patients screened will be counted. The reasons why a patient did not enter the Heart Team meeting will be collected (eg. patient does not meet inclusion criteria or meets an exclusion criteria) and, age, STS score, and available screening data.

Data readily available in the patient's medical record may be utilized to fulfill screening requirements and do not need to be repeated. If not previously completed, the following tests and procedures must be performed prior to randomization to verify eligibility. The recommended timeframe for these tests and procedures is within 30 days prior to submission to the Heart Team, unless otherwise specified.

- Demographics and Medical History
- Clinical Assessments – Refer to **Appendix R.19**
  - 5-Meter Gait Speed
  - Grip Strength
- Physical Examination including:
  - Vital signs, weight, height, and body surface area (BSA);
    - BSA will be calculated from height and weight by use of the formula by Dubois and Dubois ( $BSA = 0.007184 \times \text{weight [kg]}^{0.425} \times \text{height [m]}^{0.725}$ )
  - Major systems findings
- NYHA Classification
- Risk Assessments:
  - STS Risk Score – Dataset Version 2.73
  - Logistic EuroSCORE
  - EuroSCORE II
  - SYNTAX Score
  - Katz Index of Independence in Activities of Daily Living
- Co-morbidities
- Routine Laboratory Tests:
  - Complete Blood Count:
    - White Blood Count
    - Hematocrit
    - Hemoglobin
    - Platelet Count
  - Creatinine and Creatinine Clearance
  - Cardiac Enzymes (CK/CK-MB)
  - International Normalized Ratio (INR), if applicable
  - Activated Partial Thromboplastin Time (aPTT)
  - B-type Natriuretic Peptide (BNP) or NT-proBNP
  - Liver Panel:
    - ALT
    - AST
    - Albumin
  - Sodium
  - Potassium

- Transthoracic Echocardiogram (TTE)
  - Comprehensive transthoracic two-dimensional (2D) echocardiogram (TTE) is required within 365 days prior to review by the Heart Team to confirm diagnosis of severe aortic stenosis(AS) including:
    - Aortic valve area / indexed aortic valve area
    - Mean gradient / peak velocity / velocity ratio
  - If a historical TTE is used to confirm AS diagnosis a repeat TTE must be performed within 45 days prior to review by the Heart Team to:
    - Assess:
      - Aortic regurgitation
      - Mitral and tricuspid valve status (stenosis and regurgitation)
      - LVEF
    - Rule out:
      - New or recent MI
      - New or untreated intracardiac mass, thrombus or vegetation
      - Congenital bicuspid or unicuspid valve
  - If the patient recently underwent balloon aortic valvuloplasty (BAV), a TTE should be obtained post-BAV; within 45 days prior to review by the Heart Team to reconfirm all inclusion/exclusion echocardiographic parameters
  - Protocol required echocardiograms should be performed according to the Echocardiography Procedures found in **Appendix R.7**.
- Multi-Slice Computed Tomography (MSCT) Angiogram
  - Multi-Slice Computed Tomography (MSCT) angiograms with complete visualization of both iliacs, femorals and aorta (and subclavian/axillaries, if applicable), up to and including the aortic annulus. In the situation where subjects have compromised renal function that precludes contrast media, Magnetic Resonance (MR) imaging may be used as an alternative. MSCT angiograms should be performed according to the Computed Topography (CT) Angiography Acquisition Guidelines found in **Appendix R.9**. If the MSCT angiogram was conducted in the last 365 days and subject has not had a peripheral vascular intervention since the time of the image, a more recent exam is not required as long as visualization of both iliacs and femorals (and subclavian/axillaries, if applicable) to the aorta can be viewed. However, if the subject had a peripheral vascular intervention, the exam must be repeated after the intervention and within 90 days of review by the Heart Team.
- Coronary Arteriogram
  - Selective coronary arteriography to assess the presence and severity of coronary artery disease which should include angiograms of both coronary arteries and all bypass grafts (if applicable). If the coronary arteriogram has been performed within the last 365 days and the subject qualifies for the trial (no significant coronary artery disease), a more recent exam is not required. However, if the subject had evidence of significant coronary artery disease and/or received a coronary intervention, the exam must be repeated after the intervention and within 90 days of review by the Heart Team.
- 12-lead Electrocardiogram (ECG)

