### C.3.6 *Inclusion/Exclusion Criteria*

#### C.3.6.1 Inclusion Criteria

To participate in this trial, the subject must meet ALL of the following inclusion criteria.

1. Subject must have co-morbidities such that Heart Team agrees predicted risk of operative mortality is  $\geq 3\%$  and  $< 15\%$  at 30 days (Intermediate Clinical Risk classification). Heart team evaluation of clinical surgical mortality risk for each patient includes the calculated STS score for predicted risk of surgical mortality augmented by consideration of the overall clinical status and co-morbidities unmeasured by the STS risk calculation;
2. Heart Team unanimously agree on treatment proposal and eligibility for randomization based on their clinical judgment (including anatomy assessment, risk factors, etc.);
3. Subject has severe aortic stenosis presenting with:
  - a) Critical aortic valve area defined as an initial aortic valve area of  $\leq 1.0 \text{ cm}^2$  or aortic valve area index  $< 0.6 \text{ cm}^2/\text{m}^2$

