### C.6.8.2 Secondary Endpoints Assessed for TAVI Only

The following secondary endpoints will be assessed for the TAVI cohort subjects only:

20. Device success defined as follows:

- Absence of procedural mortality AND
- Correct positioning of a single prosthetic heart valve into the proper anatomical location AND
- Intended performance of the prosthetic heart valve (no prosthesis-patient mismatch and mean aortic valve gradient <20 mmHg or peak velocity <3 m/s, AND no moderate or severe prosthetic valve regurgitation\*)
  - Assessed acutely in a resting state, either within 24-48 hours after the index procedure or before hospital discharge

\*Refers to VARC-2 definitions

Device success, as defined above, will be calculated for all subjects undergoing the TAVI procedure.

The endpoint is descriptive and no statistical hypothesis test will be performed.

21. Procedural success, defined as device success and absence of in-hospital MACCE.

Procedural success, as defined above, will be calculated for all randomized subjects undergoing the TAVI procedure.

The endpoint is descriptive and no statistical hypothesis test will be performed.

22. Evidence of prosthetic valve dysfunction at 30 days, 6 months, 12 months, 24 months, and annually thereafter up to 5 years.

The number of subjects with evidence of prosthetic valve dysfunction will be evaluated at 30 days, 6 months, 12 months, 18 months, 24 months, and annually thereafter up to 5 years. Point estimates and 95% BCIs for each time point will be presented using methods described below in the Bayesian version of a comparison of proportions (with predictions).

23. Resheath and Recapture (combined) success rate.

The success rate will be analyzed for all subjects in whom the resheath or recapture feature is attempted. The number and percentage of successful resheath or recapture attempts combined will be calculated. Separate resheathing and recapturing success rates will also be calculated.

The endpoint is descriptive and no statistical hypothesis test will be performed.

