Diastolic flow reversal in the descending aorta—PW	Absent or brief early diastolic	Intermediate	Prominent, holodiastolic
Circumferential extent of prosthetic valve paravalvular regurgitation (%)‡‡	<10%	10-29%	≥30%
Quantitative Parameters‡			
Regurgitant volume (ml/beat)	<30 ml	30-59 ml	≥60 ml
Regurgitant fraction (%)	<30%	30-49%	≥50%
EROA (cm  )	<0.10 cm 	0.10-0.29 cm 	≥0.30 cm 

\*In conditions of normal or near normal stroke volume (50–70 mL)

†These parameters are more affected by flow, including concomitant aortic regurgitation

‡For LVOT >2.5 cm, significant stenosis criteria is <0.20

†Use in setting of BSA ≥1.6 cm^2 (note: dependent on the size of the valve and the size of the native annulus)

§Use in setting of BSA <1.6 cm^2

\*\*Use in setting of BMI <30 kg/cm^2

††Use in setting of BMI ≥30 kg/cm^2

‡‡Not well-validated and may overestimate severity compared to quantitative Doppler

Moderate or severe AS and AR will be considered a serious adverse event when the dysfunction is accompanied with clinical sequelae at the time of the event detection, and the clinical sequelae are chronologically and physiologically associated with the dysfunction.

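### The BSA formula in section C.4.1 pairs height in metres with the centimetre coefficient, so BSA as printed is 28 times too small and cannot reach the protocol's own 1.6 cut

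*Combined protocol and SAP*

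**What the plan says.** Section C.4.1 (Screening Procedures, under Physical Examination) gives an instruction, not just background: "BSA will be calculated from height and weight by use of the formula" of Dubois and Dubois. The equation that follows has coefficient 0.007184, weight in kg to the power 0.425, and height to the power 0.725 with the unit shown as [m]. The supplied text contains no other BSA formula and no unit correction.

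Quantities that depend on BSA appear in these places:

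- **Eligibility.** Inclusion criterion 3a in C.3.6.1 accepts an absolute valve area of 1.0 cm² or less, "or aortic valve area index" below 0.6 cm²/m². C.4.1 lists the indexed area among the screening echo parameters.
- **Choice of EOA limit.** In O.2, under Prosthetic Valve Dysfunction, the boundary between normal and mild stenosis is an EOA of 1.1 cm² or 0.9 cm² depending on BSA. The footnote for the first reads "Use in setting of BSA ≥1.6 cm 2". Table 2b of Appendix R.7 repeats this.
- **Prosthesis-patient mismatch.** The same tables grade mismatch by indexed EOA, with limits of 0.85 and 0.65 cm²/m² for BMI below 30, and 0.70 and 0.60 for BMI of 30 or more. Device success (C.6.8.2, endpoint 20) requires "no prosthesis-patient mismatch and mean aortic valve gradient" below 20 mmHg or a velocity criterion, among other conditions. Procedural success (endpoint 21) builds on device success.

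**The concern.** The coefficient and the unit of height do not belong together. The protocol's own figures show this without any outside source: a formula whose result stays near 0.1 m² or below cannot serve a rule that divides subjects at 1.6.

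At stake is every quantity derived by dividing by BSA or by comparing BSA with 1.6. A BSA that is too small inflates each index. An inflated index makes native stenosis look milder than the indexed criterion requires, and makes mismatch disappear. It would also place larger subjects under the EOA limits meant for smaller ones. Besides device and procedural success, the EOA limit touches prosthetic valve dysfunction (endpoint 22) and the valve-dysfunction parts of clinical efficacy and time-related safety (C.6.8.1, endpoints 5 and 6). Those two definitions give the EOA limit as a range, 0.9 to 1.1 cm². The only rule in the supplied text for choosing within that range is the BSA split.

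**Working it through.** **Inputs.** The coefficient, exponents and units are from C.4.1. The index limit of 0.6 cm²/m² is from C.3.6.1. The BSA cut of 1.6 and the EOA and indexed-EOA limits are from O.2. The protocol gives no worked BSA value to reproduce. Body sizes are assumptions, taken from 45 kg/1.50 m to 150 kg/2.00 m.

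**Step 1: BSA.** BSA = 0.007184 × weight^0.425 × height^0.725.

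| Weight, height | Height in m (as printed) | Height in cm |
|---|---|---|
| 45 kg, 1.50 m | 0.049 m² | 1.37 m² |
| 60 kg, 1.60 m | 0.058 m² | 1.62 m² |
| 70 kg, 1.70 m | 0.064 m² | 1.81 m² |
| 100 kg, 1.85 m | 0.079 m² | 2.24 m² |
| 150 kg, 2.00 m | 0.100 m² | 2.82 m² |

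The ratio is the same in every row: 100^0.725 = 28.2. If metres are kept, the matching coefficient is 0.007184 × 28.184 = 0.2025.

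**Step 2: the 1.6 cut.** At 1.70 m, the printed form reaches 1.6 only at a weight of (1.6 / (0.007184 × 1.70^0.725))^(1/0.425), about 135,000 kg. Every subject would therefore fall in the BSA below 1.6 row. That is the correct row for a subject such as 45 kg/1.50 m (true BSA 1.37 m²). It is the wrong row for anyone with a true BSA of 1.6 m² or more, who would be judged against 0.9 instead of 1.1 cm².

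**Step 3: inclusion 3a.** At 70 kg/1.70 m, a valve area of 1.0 cm² indexes to 1.0 / 0.0642 = 15.6 cm²/m² as printed, against 1.0 / 1.81 = 0.55 with centimetres. An index below 0.6 would need an area below 0.6 × 0.0642 = 0.039 cm², so the index route is closed. The practical loss is narrow, because an area of 1.0 cm² or less qualifies without any index. With the correct form, the index route adds only subjects whose area lies between 1.0 cm² and 0.6 × BSA:

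- 70 kg/1.70 m: areas from 1.0 to 1.09 cm²
- 100 kg/1.85 m: areas from 1.0 to 1.34 cm²
- 45 kg/1.50 m: none, since 0.6 × 1.37 = 0.82 cm² is already below 1.0

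**Step 4: mismatch.** At 70 kg/1.70 m the BMI is 70 / 1.70² = 24.2, so the 0.85 limit applies. As printed, mismatch needs an EOA of 0.85 × 0.0642 = 0.055 cm² or less. With centimetres it needs 0.85 × 1.81 = 1.54 cm² or less. At 150 kg/2.00 m the BMI is 37.5 and the 0.70 limit applies: 0.70 × 0.0999 = 0.070 cm² as printed, against 0.70 × 2.815 = 1.97 cm². The printed form would find no mismatch in anyone, so that condition of device success would always be met.

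**The case against.** The case for treating this as a harmless slip is substantial. The formula is named, so a reader knows which one is meant, and a BSA of 0.06 m² is implausible on sight. Units are misprinted elsewhere too: the footnotes in O.2 and Appendix R.7 Table 2b give BSA in cm² and BMI in kg/cm². A letter lost in conversion of the PDF cannot be fully excluded. The formula sits under the screening physical examination, and no section says that indexed values must be computed from it. Echo assessment is assigned to a core laboratory (C.4.10), and height and weight are entered at echo acquisition (Appendix R.7, section 5), which may be a separate source of BSA. The case report forms are under separate cover.

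All of this stands as a limit on the consequences. It does not remove the error, because the instruction as written cannot be reconciled with the 1.6 cut.

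A reader might go further and infer that every BSA-based threshold is invalid, that all subjects receive the wrong EOA limit, or that device success is overstated. The documents support none of these. The thresholds themselves are unaffected; only an input derived literally would be wrong. Subjects with a true BSA below 1.6 m² would stay in the right row. Overstatement would need the printed form to have been used, which nothing in the documents shows. In endpoints 5 and 6, valve dysfunction also rests on mean gradient, Doppler velocity index and regurgitation, so EOA is not the only determinant.

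**Conclusion.** The formula is wrong as printed. BSA comes out 28.2 times too small at any body size, and it is incompatible with the protocol's own cut of 1.6. The effects are conditional on literal use:

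- The index route in inclusion 3a would be closed, while the route through an area of 1.0 cm² or less is untouched.
- Subjects with a true BSA of 1.6 m² or more would get the 0.9 instead of the 1.1 cm² EOA limit.
- Mismatch would never be found, so device and procedural success could only be biased upward.

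The size of that last bias cannot be given, since the documents state no mismatch rate. Both success rates are descriptive, with no hypothesis test. C.6.10.1 allows them in the labelling but without statistical claims.

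A reader might also infer a threat to the trial's main conclusions. There is none: the primary endpoint of death or disabling stroke, the sample size and the tests in the labelling hierarchy do not use BSA. The hierarchy tests absolute EOA and mean gradient, not indexed EOA.

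The conclusion assumes that the unit in the source document is [m], as in the supplied text. The body sizes are illustrative, and no plausible adult size changes the result.

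**What to change.** 1. Compare C.4.1 with the source PDF, then print height in cm. Alternatively, keep metres and change the coefficient to 0.2025.
2. In the footnotes to the prosthetic valve dysfunction table in O.2 and to Table 2b in Appendix R.7, change the BSA unit from cm² to m² and the BMI unit from kg/cm² to kg/m². The indexed limits in cm²/m² already imply the former, and exclusion criterion 29 already uses the latter.
3. Confirm that the electronic data capture and core-laboratory derivations use the correct form. Recompute indexed values only if that check finds an error.

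The cost is a one-line correction, the footnote units and one derivation check. No clinical threshold changes.

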### C.4.2 Heart Team Procedures

Each center will utilize a Heart Team to make determinations regarding eligibility of the prospective subject to be randomized in the SURTAVI trial.

#### C.4.2.1 Heart Team Composition

Local Heart Teams must be comprised of a multidisciplinary team qualified by education and experience to determine appropriate patient treatment.

##### **Minimum Membership**

- Interventional Cardiologist - ≥ 1 representative is required
- Cardiac Surgeon - ≥ 1 representative is required

##### **Additional Membership Considerations**

Additional members of the Heart Team should be included based on current standard practices and patient specific consideration, including but not limited to:

- Echocardiographer
- Anesthesiologist
- Cardiologist (general or referring physician)
- Geriatrician
- Neurologist or stroke specialist
- Radiologist or imaging specialist
- Heart Failure specialist
- Intensivist
- Nurse(s)
- Social Worker

#### C.4.2.2 Heart Team Review and Decision

Prior to determining if a patient is eligible for randomization the Heart Team will review each patient's screening data and confirm the following:

- STS risk calculation was properly performed
- Any additional risk factors not accounted for in the STS risk calculator that may increase the level of surgical risk:
  - Heart Team should consider the following potential incremental risks:
    - Age ≥ 75
    - BNP ≥ 550pg/mL or NT proBNP ≥ 3200pg/mL
    - Prior Stroke/TIA
    - FEV1 750-1000cc
    - Home / Supplemental oxygen
    - Nocturnal Bi-level Positive Airway Pressure
    - 5-Meter Gait Speed ≥ 6 seconds
    - Severe Diastolic Dysfunction (Grade III or IV)
    - Liver Disease (Child A or B)
    - Pulmonary Hypertension (systolic pressure 60-80mmHg)
    - Frailty (eg. BMI <21 kg/m^2, Albumin <3.5 g/dL, etc.)
    - Other risks, as deemed applicable
  - Confirm the incremental risk, as determined by the Heart Team, does not result in a risk definition higher than intermediate risk
- All inclusion criteria are met and none of the exclusion criteria

Both the reviewing Interventional Cardiologist and Cardiac Surgeon(s) must unanimously agree the patient has a predicted risk of operative mortality ≥ 3% and < 15% and appropriate for trial enrollment. The decision of the local Heart Team must be documented on the "Heart Team Decision" form and signed by the reviewing Interventional Cardiologist and Cardiac Surgeon(s).

---

 US only - Protocol criteria for Heart Team approval may not meet the minimum requirements outlined by Centers for Medicare and Medicaid Services (CMS) for reimbursement. Reference **Appendix R.25** for additional information.

### C.4.3 Screening Committee

The Screening Committee will ensure appropriate and consistent patient selection across all sites. Prior to the onset of the trial, a charter will be drafted to that outline roles and responsibilities as well as describe the Screening Committee process.

Final decisions on patient eligibility will be made by the Screening Committee.

### C.4.4 Roll-in Subjects

For participating centers who meet the requirement of 30 cumulative TAVI procedures but have no previous CoreValve experience (eg. Investigational centers where CoreValve is not commercially available and/or centers that did not participate in the US Pivotal Extreme/High Risk protocols) the first three successfully enrolled subjects will be considered “roll-in” subjects, will not be randomized, and will automatically be assigned to TAVI. A maximum of three successful roll-in subjects are allowed per center.

The purpose of the roll-in subjects is to provide investigators the time for training and familiarization with the investigational TAVI device. The Training and Education team will review recommendations made by Medtronic field support, Medtronic CoreValve Proctors and the Steering Committee for transition of sites from the roll-in phase to the randomization phase of enrollment after the first three subjects have been treated.

A subject will be considered a treated roll-in subject once the TAVI delivery catheter system (DCS) is introduced into the subject. A site must have three treated roll-in subjects before they can be evaluated to move into the randomization phase. The Training and Education team or designee will review and document their decisions based on the technique of the investigators, as well as the frequency, severity and nature of events in the roll-in subjects.

Roll-in subjects will complete in-clinic follow-up evaluations at the following time points post implant as subjects randomized to TAVI. However, the results for the roll-in population will be analyzed separately from the randomized population.

